However, numerous methodological and contextual limitations exist within the context of pain management centres that are increasingly providing mindfulness based interventions to pain sufferers. This has potential implications for whether implementing mindfulness skills is done with clarity, good governance about whether, where and how it is helpful, or whether it even can be harmful, duplicate other treatments or unnecessarily burden pain sufferers with something that is not needed. In this context, it also has significant implications on any required development of teachers' competencies.

No current research has attempted to unify ACT and other mindfulness process measurement (how people get to change – as opposed to what change they achieve) or to establish the potential contribution and relevance of different specific mindfulness courses in chronic pain patients' treatment pathways and outcomes.

A community-based multidisciplinary-pain-management naïve sample (N=100) of chronic pain patients will be recruited in primary care and placed on a time-set waiting list and then randomly allocated to **one** of two standardised active online mindfulness treatments - stress **or** pain group

conditions. Measurement will include theoretically validated process and outcome measurement. Treatment adherence and fidelity will be independently evaluated from recorded sessions and inter-rater agreement checks performed.

Quantitative analysis will be performed to include descriptive statistics, analysis of variance, session-by-session process change trends, and post-hoc analysis on GP and A&E visits.

Qualitative thematic analysis will complement and bolster the findings of the quantitative phase to include additional process variables unaccounted for by the ACT model, patient experience and descriptive comparison of the two active conditions, including descriptive statistics comparing frequency of reported themes between the two treatments.

i. Aims and objectives:

This study aims to explore and better understand the contribution of standardised group-based mindfulness courses to theoretically valid and coherent mindful-change processes.

OBJECTIVES

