7. Patients who are actively suicidal, terminally ill or have dementia, cognitive impairment, learning difficulties, or the GP knows of another reason to exclude.

ETHICAL ISSUES

Informed consent

We will obtain approval to contact practices regarding the study with participant's information leaflet and GP information leaflet. We will also obtain informed consent from the treatment providers, including in relation to video/audio feed being recorded. Participants will be offered opportunity to switch off their cameras.

Confidentiality

Data will not be accessed outside the research team. Once collected, checked for inclusion criteria and allocated to a randomly generated participant number, data will be anonymised and prior to the off-site transfer for blind analysis (the statistician will not be aware of which condition stress/pain the participants have been allocated to). Data Transfer Protocols will be utilised in line with the Government of Jersey Governance and Data Protection system, to transfer the data ahead of analysis.

A participant waiting-list randomised, pilot trial of mindfulness based group treatment comparing two active interventions (stress vs pain mindfulness courses) and the waiting-list at recruitment time and 8-weeks post recruitment, coinciding with the start of treatment.

Randomisation will be based on computer-generated random numbers and the sample randomised, will act as a pseudo-waiting-list control for the eight-week waiting period ahead of the intervention.

Recruitment details and Participants

PARTICIPANTS AND DATA COLLECTION

100 people with chronic pain (defined as > three months duration) will be recruited from primary care and social media adverts in Jersey (the social media participants will be

required to register their interest via their GP who will then refer to the lead researcher). Once recruited, participants will be required to complete baseline outcome and process measures, 8-weeks ahead of beginning their 8-week course. Randomisation will take place at this point to either the stress or the pain course. They will repeat this assessment on week 1 of the course and then again at week 4. They will also complete only process measures weekly during the course, in order to explore for links between weekly course content and specific process change.

Posttreatment assessment will be completed within four weeks of treatment completion and at 3-month follow up.

How this study will improve on previous research

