An opportunity sample from all patients invited to take part to the quantitative research aspect, invited as part of the initial quantitative study informed consent process.

We will invite all participants from the sample, aiming from 10-15 participants from each the stress and pain version of the courses, hence a total sample of 30 participants maximum and a target of 10 completed interviews for each intervention.

iv. Proposed method(s) of data analysis

Quantitative:

PRELIMINARY ANALYSIS

After randomisation, we will carry out preliminary baseline analysis using independent group t-tests to establish no significant demographic (age, education, duration of pain, number of comorbid medical conditions, visits for pain the past three months) or psychometric differences between the groups. This will act as a pseudo-waiting list treatment-as-usual (TAU) control group.

MAIN ANALYSIS

Treatment process change and outcomes

Means, Standard Deviations (SDs), between-group analysis of variance and co-variance (ANOVA, Between-Group ANCOVA) results and effect sizes (Between-Group effect sizes: d) for pretreatment, session-by session process change tracking including a practical selection of accepted and validated process-change measurement for all six areas of psychological flexibility and outcome measurement related to:

- pain intensity and interference
- impact on functioning
- emotional functioning (depression, pain catastrophizing)
- Global impression of functioning

for baseline, half-way, end-of-treatment and follow up

Analysis will be performed utilising SPSS.

These will include a practical selection of primary outcome measures, treatment process measures, as well as measures of emotional functioning, patient rating of change and change in medication use.

Post-hoc analysis

Will include number of GP and A&E visits comparing the waiting period and from the end of treatment to follow up.

STATISTICAL POWER

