iv. Are there any potential risks or adverse effects to *researchers themselves*?

Given the open recruitment via social media, there is the potential risk of unknown participants' forensic or problematic history. However, this will be mitigated by requesting all participants seek to access the research project via initial contact with their GP surgeries.

v. Where samples will be taken from the participant, please state which samples, the amount and frequency of them and whether the sample would be taken as part of the normal patient care or specifically for the purposes of the research? If a sample would normally be taken as part of usual patient care - will the amount taken be any greater due to the participation of the participant in the research?

Not applicable

vi. Where the research involves the use of radioactive isotopes, please confirm that the dosage proposed to be used in the research has been approved by a Radiological Safety Committee or Administration of Radioactive Substances

Advisory Committee (ARSAC), and that the person(s) who will administer the dose is/are properly qualified and hold(s) the necessary certificate(s)?

Not applicable.

- vii. Where the research involves the testing of a medicinal product (or medical device), please state the regulatory status of the drug/device in question. Is the research being conducted under the terms of a product licence, Clinical Trials Certificate (CTC), Clinical Trials Exemption (CTX) or Doctor's and Dentist's Exemption (DDX)?**

Not applicable.

- viii. Please indicate whether participants will receive payment or reimbursement for taking part in the research study (including reimbursement of expenses). If so, what amount?**

Not applicable.

- ix. Please state the relationship, if any, which may/will exist between the researcher(s) and potential participants. (Eg. will any of the participants be students, subordinates or colleagues of the investigator, or staff members of the University?)**

Not applicable. However, given the nature of Jersey, participants may be known to the research team, may be acquaintances or fellow colleagues. This is unavoidable.

4. Informed consent:

Will informed consent be obtained from the research participants?

Yes No

If 'YES', please give details of who will obtain consent and how this will be done, including how long participants will have to decide whether or not to take part. If 'NO', please explain why not.

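### GP and A&E visits are compared before versus after over unequal windows, with no arm contrast stated, so visits can appear to rise or fall with no course effect

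*Combined protocol and SAP*

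**What the plan says.** - **The visit analysis.** Part 3, section 2.iv, under Post-hoc analysis, covers the "number of GP and A&E visits comparing the waiting period and from the end of treatment to follow up". The scientific abstract adds only a "post-hoc analysis on GP and A&E visits". Neither names an arm comparison, a model, a rate, or a rule for what counts as a visit.
- **The between-arm analyses.** Under Main analysis in the same section, ANOVA and ANCOVA are planned for the process measures and a list of outcomes. Visits are not on that list. The one stated comparison of visits between arms is a baseline check on "visits for pain the past three months".
- **The windows.** Section 2.iii has baseline completed "8-weeks ahead of beginning their 8-week course". On the later assessments it says: "Posttreatment assessment will be completed within four weeks of treatment completion and at 3-month follow up".
- **The control.** The randomised sample "will act as a pseudo-waiting-list control for the eight-week waiting period ahead of the intervention". There is no concurrent untreated arm.
- **Entry.** People who respond to social media are "required to register their interest via their GP who will then refer to the lead researcher". Section 3.iv describes "requesting all participants seek to access the research project via initial contact with their GP surgeries".

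**The concern.** The trial asks what each of two courses contributes, and randomisation supports a comparison of one course with the other. For visits, the stated comparison does not use it. It sets the same people's earlier period against a later one, so anything that changes over time is mixed with the effect of the course.

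Two such influences can be seen in the plan. First, the later window is longer, which inflates later raw counts. Second, people enter through their GP, some of them after waiting-room adverts. Contacts made in order to enter, or a spell of frequent consulting around entry, could raise the early count if they carry over into the wait. The two influences push in opposite directions, and converting to rates removes only the first.

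At stake is the reading of the service-use result. GP visits appear in the lay abstract among the things the study hopes to learn about. Because the wait is described as a control, a before-after change could be taken for a controlled finding.

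**Working it through.** The plan gives no visit rate, alpha or power for this analysis, so there is no figure of its own to reproduce. The check asks what the stated comparison shows when the courses do nothing.

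**Inputs from the plan.** The wait is 8 weeks. Follow-up is at 3 months, about 13 weeks from the end of treatment. If the 3 months run from a post-treatment assessment held up to 4 weeks later, the window is up to 13 + 4 = 17 weeks; the start of the clock is not stated. Recruitment is 50 per arm, with a minimum target of 30.

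**Assumptions, not in the plan.** A true mean of m visits per 8 weeks (0.5, 1 or 2), and f extra entry-related visits per person inside the wait (0 to 1). The simulation uses 4 to 12 visits per year, gamma-Poisson counts with dispersion 1, two-sided 0.05 and 4,000 runs per scenario.

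**Step 1: window length alone (f = 0).** The ratio of raw counts is 13/8 = 1.625, a rise of 62.5%. With 17 weeks it is 17/8 = 2.125. A true fall in rate of 1 − 8/13 = 38% would leave raw counts level. At 8 visits per year and 50 per arm, a paired test on raw counts showed a significant rise in 99% of runs and a significant fall in none.

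**Step 2: entry contacts on a rate scale.** The apparent fall is f/(m + f). With m = 1:
- f = 0.25: 0.25/1.25 = 20%
- f = 0.5: 0.5/1.5 = 33%
- f = 1: 1/2 = 50%

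At 8 visits per year, m = 8 × 8/52 = 1.23, and the falls are 17%, 29% and 45%. With 50 per arm they were significant in 38%, 92% and 100% of runs. With f = 0, a significant change in either direction came up in about 5%.

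**Step 3: both together on raw counts.** The ratio is 1.625m/(m + f), with a 13-week later window.

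| m | f = 0.25 | f = 0.5 | f = 1 |
|---|---|---|---|
| 0.5 | +8% | −19% | −46% |
| 1 | +30% | +8% | −19% |
| 2 | +44% | +30% | +8% |

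Six of the nine cells rise. With 17 weeks (2.125 in place of 1.625), eight of nine rise. With r visits per week, a raw fall needs 13r < 8r + f, so r < f/5. That is fewer than 10.4 visits per year for f = 1, 5.2 for f = 0.5 and 2.6 for f = 0.25.

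**Step 4: the arm contrast.** Later visits compared between arms, adjusted for waiting-period visits, gave false positives in 4.2% to 5.3% of runs in every scenario. Both arms share the windows and the entry route, so these cancel. Unadjusted, the difference detectable with 80% power is (1.96 + 0.84) × √(2/n): 0.56 SD at n = 50 and 0.72 SD at n = 30. Power for d = 0.5 is 71% and 49%.

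**The case against.** The strongest objection is about timing. In section 2.iii the GP registers and refers the person first; recruitment and baseline follow, and the 8-week wait starts there. The eligibility step is described as a search of GP records, not an attendance, and an initial contact with a surgery need not be a consultation. A reader might infer from the GP entry route that visits will falsely fall. The documents do not support that: nothing places an entry contact inside the wait, and raw counts lean towards a rise. What remains is a possibility. The records search comes after consent, the plan does not say whether recruitment is dated from consent, referral or baseline, and no rule says which contacts count.

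A reader might also infer that visits will not be compared by arm. That rests on silence: the text lists what the post-hoc analysis will include and excludes nothing. Nor does the plan say it would report a fall as reduced service use; it is a pilot, makes no formal predictions and labels this item post-hoc. The baseline check on pain visits is a comparability check between arms. It is not the before term of this comparison and does not bias it.

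Lastly, pain versus stress cannot show that either course lowers visits. This is correct and is a limit of the design. The before-after figure cannot show it either.

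**Conclusion.** The point holds as one of attribution, without a fixed direction. The only stated analysis of visits as an outcome is uncontrolled, runs over windows of 8 and about 13 (possibly up to 17) weeks, and states no arm contrast. With no course effect, raw counts would rise by about 62.5% at a constant rate. That figure rests only on the window lengths and a 3-month clock starting at the end of treatment. On a rate scale, a fall of 20% to 50% could appear, but only if 0.25 to 1 entry-related visit per person, or a comparable excess from a high-consulting period, lies inside the wait on a mean of 1. Those inputs are assumed.

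The item is secondary and labelled post-hoc, so the main process and outcome comparisons are unaffected. The change is still worth making because it uses data and groups the trial already has.

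**What to change.** 1. State the start and end of both windows, including where the 3-month clock begins, and analyse visits per week, or use a count model with the log of each person's observed weeks as offset.
2. Define a visit once (GP plus A&E) and use that definition in both windows. Do not count contacts made only to register, be referred or confirm eligibility.
3. State the arm contrast: follow-up visit rate, pain versus stress, adjusted for each person's waiting-period rate, reported as an estimate with a CI.
4. Keep the before-after figure as description, and say that an overall change cannot be attributed to the courses because no arm is untreated.

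The cost is one data-collection rule and one model, with no extra assessments. The drawback is the imprecision shown above, and the contrast answers only whether the two courses differ. Leaving out entry contacts does not remove regression from a high-consulting period in the before-after figure, which is a further reason to keep that figure descriptive.

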4) *Cognitive fusion:* the Cognitive Fusion Questionnaire (Gillander *et. al*, 2014)

5) *Values:* The Chronic Pain Values Inventory (McCracken and Yang 2006)

6) *Committed Action:* The 8-item Committed Action Questionnaire (McCracken, Chilcot et al. 2015)

Outcome measures:

Pain Intensity and interference on quality of life : the Brief Pain Inventory – Short Form (Tan, Jensen et al. 2004), numeric rating scale (NRS) on intensity (scale 0-10) including, worst, least

average (in the past week) and right now. BPI interference scale for impact on quality of life.

Emotional Functioning

a. *Pain related distress:* The Pain Catastrophizing Scale (Sullivan, Bishop et al. 1995)

b. *Depression:* The Beck Depression Inventory – Fast Screen (Poole, Bramwell et al. 2009)

Global Impression of Functioning: the Patient's Global Impression of Change (Guy 1976) will allow to consider perceived improvement and deterioration.

Qualitative:

DATA ANALYSIS

Transcribed data will be managed with NVivo software. All transcripts will be read and reread to ensure familiarity with the data. We will use thematic analysis (Braun and Clarke 2006) to identify recurring themes across the data and examine relationships between themes. The thematic analysis will be undertaken by two researchers independently coding for emerging themes and then comparing codes and themes.

TOPIC GUIDE

Do you have any previous experience in taking part in clinical trials or medical research?

I'm really interested in finding out what were your initial expectations and feelings about the mindfulness course?

What do you feel you have gained from attending the course?

What (if any) changes have you noticed in your health/quality of life? [probe for anything getting better or worse: health, emotional, physical, practical]

How do you feel the course has contributed to how you manage chronic pain?

This study has involved you doing some reading, meditation and practices in everyday life ('habit releasers'). Would you give me a sense as to whether you have managed to engage in these practices? [Ask about how long typically they have practiced daily formal meditation; are they still practising?; What has stuck and what hasn't?]

Is there anything else you would like to say about your experience of the course?

How do you feel the teacher contributed to your experience of the course?

What contribution do you feel the group has made to what you have learnt?

Since attending the course:

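### The global change rating is included to show improvement and worsening, but the plan analyses it by means, ANOVA/ANCOVA and d, where the two can offset each other

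*Combined protocol and SAP*

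**What the plan says.** All references are to Part 3, section 2, of the combined protocol and SAP.

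- **Purpose of the rating.** Under Outcome measures (2.iv), the Patient's Global Impression of Change is included because it "will allow to consider perceived improvement and deterioration". The response scale and the categories that count as worse are not given.
- **Planned analysis.** Main Analysis (2.iv) opens with "Means, Standard Deviations (SDs), between-group analysis of variance and co-variance" and between-group d. The outcomes it covers are listed as bullets, and the last bullet is "Global impression of functioning". The time points are given as "for baseline, half-way, end-of-treatment and follow up". A later sentence mentions patient-rated change again but names no method for it.
- **Other quantitative wording.** The scientific abstract names "descriptive statistics, analysis of variance, session-by-session process change trends" and a post-hoc look at GP and A&E visits. It does not mention category counts for this rating.
- **Where direction is counted.** Qualitative question (c), under the research questions, asks how often themes appear in each group and whether they point to better, worse or unchanged. That applies to interview themes only. Interviews are limited to 30 people in total (Sampling) and exclude anyone who attended fewer than 6 of 8 sessions (Qualitative study, exclusion criteria).
- **Sample size.** Procedure (2.iii) gives 50 recruited per course, with a minimum of 30. The Statistical Power section declines to give a power calculation.

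**The concern.** The purpose and the method do not match. The useful information in a single ordered change item is how many people chose each category. A mean reduces this to one number in which an improvement of two points cancels a worsening of two points. Two courses can therefore have the same mean and d near zero while quite different shares of participants say they are worse.

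If the plan is followed as written, the report could show no difference on the one outcome chosen partly to show deterioration, and a reader could not tell how many people on either course felt worse. The interviews do not fill the gap. They cover a minority of participants and leave out non-completers, who may include people who stopped because they felt worse.

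**Working it through.** The plan gives no figure to reproduce: no alpha, effect size, SD or response distribution. The check asks whether the planned summaries could miss a difference in the share worse, and how precisely that share could be estimated.

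**Inputs.** From the documents: 30 and 50 per course. Assumed: a 7-point scale (1 best, 4 no change, 7 worst), two-sided alpha 0.05, and the response distributions below.

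**Case 1: same mean, different share worse** (scores 2, 3, 4, 5, 6)
- Course A: 5%, 10%, 70%, 10%, 5%. Mean = 0.10 + 0.30 + 2.80 + 0.50 + 0.30 = 4.00. Worse = 10% + 5% = 15%.
- Course B: 20%, 15%, 30%, 15%, 20%. Mean = 0.40 + 0.45 + 1.20 + 0.75 + 1.20 = 4.00. Worse = 15% + 20% = 35%.
- d = 0. In 20,000 simulated trials, ANOVA rejects in 4.8% (30 per course) and 5.3% (50 per course), that is, at its error rate. The SDs are 0.77 and 1.38.

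**Case 2: same share better, different share worse**
- Course C: 10%, 35%, 20%, 15%, 10%, 10% on scores 1 to 6. Mean = 0.10 + 0.70 + 0.60 + 0.60 + 0.50 + 0.60 = 3.10. Better 65%, worse 20%.
- Course D: 20%, 45%, 30%, 5% on scores 2 to 5. Mean = 0.40 + 1.35 + 1.20 + 0.25 = 3.20. Better 65%, worse 5%.
- SDs are 1.48 and 0.81, so d = (3.10 − 3.20) / √[(1.48² + 0.81²)/2] = −0.08. The course with four times the worsening has the slightly better mean. ANOVA rejects in 7.1% and 7.7% of trials.

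**Would an ordinal test do better?**
- Take course E with 60% scoring 2, 20% scoring 4 and 20% scoring 6, and course F with 80% scoring 3 and 20% scoring 4.
- Means: 1.2 + 0.8 + 1.2 = 3.2, and 2.4 + 0.8 = 3.2. Worse: 20% and 0%. SDs: 1.6 and 0.4.
- P(E better than F) = 0.60. P(F better than E) = 0.20 + 0.20 × 0.80 = 0.36.
- In simulation the t-test rejects in about 6% of trials. Wilcoxon rejects in about 44% (30 per course) and 57% (50 per course), and over 99% of those rejections favour course E, the one with 20% worse. A proportional-odds fit leans the same way. In Case 1, Wilcoxon rejects in only about 6%.

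**Precision of the share worse.** The exact (Clopper-Pearson) limits for k of n are the 0.025 quantile of Beta(k, n − k + 1) and the 0.975 quantile of Beta(k + 1, n − k).

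| Worse | Share | Exact 95% CI |
|---|---|---|
| 3/30 | 10% | 2.1% to 26.5% |
| 5/50 | 10% | 3.3% to 21.8% |
| 6/30 | 20% | 7.7% to 38.6% |
| 10/50 | 20% | 10.0% to 33.7% |

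If nobody is worse, the upper limit is 1 − 0.025^(1/n): 11.6% at 30 and 7.1% at 50.

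**Power for a formal test of the share worse, 20% versus 5%.** Power = Φ{[|p1 − p2|√n − 1.96√(2p̄(1 − p̄))] / √[p1(1 − p1) + p2(1 − p2)]}, with p̄ = 0.125.
- n = 50: (1.061 − 0.917)/0.456 = 0.32, so 62%.
- n = 30: (0.822 − 0.917)/0.456 = −0.21, so 42%.
- 80% power needs 76 per course.

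The comparison can only be descriptive.

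**The case against.** Several counter-arguments have force.

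- **The planned SDs would give a hint.** They differ in every example above. This stands in part: a wider spread is a signal, but an SD shows neither direction nor how many people worsened.
- **The Main Analysis sentence is loose, and general descriptive statistics could include frequencies.** True, but none are specified for this rating, and the section that spells out the analysis names means and SDs.
- **Worsening is looked for elsewhere.** The protocol commits to reporting adverse side effects, asks participants to tell facilitators about significant difficulties, and probes for worsening at interview. This stands in part. None of it is a count by course from the rating itself, and the interviews omit non-completers.
- **The examples are constructed.** This stands. The scale and every response rate are assumptions, and whether improvement and worsening offset each other depends on the data.

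A reader might also infer that the trial's harm question would be answered wrongly. The documents do not support that. The remark about "whether it even can be harmful" in the scientific abstract is background on pain centres adopting mindfulness. Harm is not among the objectives or the quantitative research questions, and no section says it will be judged from this rating.

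**Conclusion.** The point holds as a mismatch between a stated purpose and a stated method. The rating is there to consider improvement and deterioration, the planned summaries allow one to offset the other, and no count of people who worsened is specified outside the interviews.

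On assumed distributions, a 15- to 20-point difference in the share worse can sit beside d between 0 and 0.08 in size, with ANOVA rejecting in about 5% to 8% of trials. This shows what can happen, not what will. It does not show that the plan is blind to all deterioration.

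Two further inferences should be resisted. First, an ordinal test is not the cure: Wilcoxon and proportional-odds methods also let improvement offset worsening, and can favour the course with more people worse. Second, counting every rise in BDI-FS or BPI interference as deterioration is not a sound supplement, because without a threshold it would report measurement noise as harm.

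**What to change.** In Main Analysis (2.iv), take the global rating out of the mean/ANOVA/ANCOVA/d list and specify instead, by course, at end of treatment and at 3-month follow-up:

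1. the response categories, and which of them count as worse, fixed before analysis;
2. n (%) in each category;
3. the share in any worse category, with an exact 95% CI;
4. the between-course difference in that share, with a 95% CI by a named method;
5. the number without a rating, with non-completers included wherever they gave one.

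Label this as descriptive. Do not substitute a Wilcoxon or proportional-odds test, and do not add a count of any BDI-FS or BPI worsening.

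The cost is a few lines of analysis text and one small table, with no new data collection. The downside is that the intervals will be wide and will look less reassuring than a mean, but they show fairly what 30 to 50 people per course can say.
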